2.1 Background & Aims

Healthcare professionals are required to integrate foundational physiological knowledge with clinical reasoning to ensure safe and effective patient care. A persistent challenge in health sciences education is the gap between students' ability to recall physiological concepts and their capacity to apply this knowledge meaningfully in clinical decision-making contexts. This theory-practice disconnect has been consistently reported across nursing and allied health education and is associated with reduced clinical preparedness and learner confidence.

Traditional preclinical physiology education commonly relies on curriculum-based instructional approaches centered on didactic teaching, textbook-directed learning, tutorials, and laboratory practical activities. Although such approaches may facilitate short-term knowledge acquisition, they are often insufficient for promoting higher-order cognitive processes, including interpretation, integration, and application of physiological principles in clinical contexts. Consequently, students may demonstrate adequate theoretical understanding yet experience difficulty explaining physiological mechanisms underlying patient presentations or justifying clinical decisions.

Aims of this study:

- To evaluate the effectiveness of AI-assisted algorithm-supported adaptive screen-based simulation compared with conventional physiology instruction on physiological knowledge acquisition and reasoning ability among undergraduate health science students.
- To assess the impact of the intervention on secondary outcomes including conceptual understanding, learning engagement, cognitive load, and academic self-efficacy at post-intervention and four-week follow-up.

2.2 Background Literature Review

Simulation-based education has emerged as an effective pedagogical approach to bridge the gap between theoretical knowledge and clinical application by enabling experiential, learner-centered engagement in realistic clinical scenarios. Among available simulation modalities, screen-based simulation offers particular advantages for physiology education, as physiological processes are inherently dynamic and often not directly observable during routine clinical encounters.

Recent advances in adaptive educational technologies have expanded the capabilities of simulation-based learning. Rule-based adaptive simulation systems can dynamically adjust case complexity, sequence learning activities, and provide automated formative feedback according to learner performance. These adaptive features support individualized learning pathways and are aligned with established educational theories including experiential learning, cognitive load management, and self-efficacy development.

Despite increasing interest in AI-assisted educational technologies, robust empirical evidence evaluating their effectiveness in foundational science education, particularly physiology, remains limited. Existing studies have largely focused on feasibility, usability, or learner satisfaction rather than objective learning outcomes derived from rigorous experimental designs.

Theoretical Framework: This study is grounded in:

- **Experiential Learning Theory** (Kolb, 2014): Learning through doing and reflection in simulation environments.
- **Cognitive Load Theory** (Sweller, 2020): Managing intrinsic, extraneous, and germane cognitive load to optimize learning.
- **Self-Efficacy Theory** (Bandura, 1977): Mastery experiences in adaptive simulation enhancing learner confidence.

3. Study Protocol

3.1 Research Design Outline

This study was designed as a **prospective, two-arm, parallel-group randomized controlled trial (RCT)** with repeated-measures assessment at three predefined time points:

- **Time 1 (Baseline):** Week 1, prior to intervention commencement
- **Time 2 (Post-Intervention):** Week 13, immediately following the 12-week intervention
- **Time 3 (Follow-up):** Week 17, four weeks post-intervention

The trial was conducted at **Saveetha Institute of Basic Medical Sciences (SIMATS), India**, between **August 2025 and January 2026**.

The study was designed and reported in accordance with the **Consolidated Standards of Reporting Trials (CONSORT) 2010 guidelines**. The intervention description additionally followed the **Template for Intervention Description and Replication (TIDieR) checklist** and the **INACSL Healthcare Simulation Standards of Best Practice**.

3.2 Participants

Undergraduate health science students enrolled at Saveetha Institute of Basic Medical Sciences, India, registered for a Human Physiology course during the study period (August 2025 - January 2026) were eligible for participation.

Study Setting: Saveetha Institute of Basic Medical Sciences, SIMATS, Chennai, India.

Programs included: Physiotherapy, Occupational Therapy, Nursing, and Allied Health Sciences.

3.3 Sample Size Determination

Sample size estimation was performed using **G*Power version 3.1.9.7** for repeated-measures analysis of variance (ANOVA) with a within-between interaction.

Parameters assumed:

- Effect size: medium ($f = 0.25$)
- Type I error rate (α): 0.05
- Statistical power: 0.95
- Number of groups: 2
- Measurement occasions: 3
- Correlation among repeated measures: 0.5

Calculated minimum sample: 292 participants per group.

Final target enrollment: 336 participants per group (accounting for an anticipated 15% attrition rate), yielding a **total sample size of 672 participants**.

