3.8.2 Secondary Outcomes

3. Conceptual Understanding (Physiological Concepts Inventory - PCI)

- Faculty-developed physiology concept inventory distinguishing deep conceptual understanding from surface-level memorization
- Covers all 8 physiological systems
- Cronbach's $\alpha = 0.84$ (good internal consistency)
- Higher scores indicate deeper conceptual understanding
- Time Frame: Baseline, Post-Intervention, 4-week Follow-up

4. Student Engagement (University Student Engagement Inventory - USEI)

- Assesses behavioral, emotional, and cognitive dimensions of learner engagement
- Higher scores indicate greater engagement
- Cronbach's $\alpha = 0.88$
- Time Frame: Baseline, Post-Intervention, 4-week Follow-up

5. Cognitive Load (NASA Task Load Index - NASA-TLX)

- Multidimensional measure of perceived cognitive workload
- Higher scores reflect greater perceived workload and task demand
- Cronbach's $\alpha = 0.82$
- Time Frame: Baseline, Post-Intervention, 4-week Follow-up

6. Academic Self-Efficacy (College Academic Self-Efficacy Scale - CASES)

- Adapted version assessing learner confidence in physiology-related academic tasks and simulation-based learning activities
- Higher scores indicate greater academic self-efficacy
- Cronbach's $\alpha = 0.86$
- Time Frame: Baseline, Post-Intervention, 4-week Follow-up

4. Statistical Analysis Plan (SAP)

All statistical analyses were performed using **IBM SPSS Statistics version 22.0** (IBM Corp., Armonk, NY, USA). All tests were two-tailed, with statistical significance set at $\alpha = 0.05$.

Effect size conventions:

- Cohen's d / f : 0.20 (small), 0.50 (medium), 0.80 (large)
- Partial eta squared (η^2p): 0.01 (small), 0.06 (medium), 0.14 (large)

All randomized participants were included in final analyses according to the **intention-to-treat (ITT) principle**.

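### The inputs listed in section 3.3 give 44 participants in total (up to about 212 under unstated options), not 292 per group, so the basis of the sample size is undocumented

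*Combined protocol and SAP*

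**What the plan says.** Section 3.3 reports a calculation in "G*Power version 3.1.9.7" "for repeated-measures analysis of variance (ANOVA) with a within-between interaction". The inputs are a medium effect of f = 0.25, "Type I error rate (α): 0.05", power 0.95, two groups, three occasions and "Correlation among repeated measures: 0.5". The result is "Calculated minimum sample: 292 participants per group", raised to 336 per group (672 in total) for 15% attrition. The section gives neither a nonsphericity correction nor the effect-size option.

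Section 4.1 makes repeated-measures ANOVA, with its time-by-group interaction, the primary analysis for both primary outcomes. It provides a Greenhouse-Geisser correction if sphericity fails. The opening of section 4 gives the effect-size conventions as "Cohen's d / f : 0.20 (small), 0.50 (medium), 0.80 (large"), followed by partial eta-squared cut-offs of 0.01, 0.06 and 0.14.

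**The concern.** A sample-size section should let a reader with the named software recover the number and know what effect the trial can detect. Here every main input is listed, the test matches the planned primary analysis, and the answer is still far from the stated one. The pairing of 95% power with f = 0.25 therefore does not describe a trial of this size, and nothing in the documents shows what effect the enrolment target was chosen to detect. At stake is whether the design rationale can be traced, not the validity of the analysis.

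**Working it through.** **Inputs.** From section 3.3: f = 0.25, alpha = 0.05, power = 0.95, k = 2 groups, m = 3 occasions, rho = 0.5. From section 3.5: 1:1 allocation. Not stated, so assumed and varied: epsilon (1, and its minimum of 0.5 for three occasions) and the effect-size option.

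**Stated inputs, default option, epsilon = 1.** The interaction F test has noncentrality lambda = f²·N·m·epsilon/(1 − rho), with df1 = (k − 1)(m − 1)·epsilon and df2 = (N − k)(m − 1)·epsilon.

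- N = 42: lambda = 0.0625 × 42 × 3/0.5 = 15.75, df 2 and 80, power 0.946.
- N = 44: lambda = 0.0625 × 44 × 3/0.5 = 16.5, df 2 and 84, power 0.956.

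An odd total of 43 reaches 0.951, which equal groups round up to 44, or 22 per group. The plan's figure is 2 × 292 = 584, and 584/44 = 13.3.

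**Can another setting recover 584?** Each row keeps f = 0.25, alpha 0.05 and power 0.95.

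| Setting | Total N |
|---|---|
| Default option, epsilon 1 | 44 |
| Default option, epsilon 0.5 | 72 |
| Default option, correlation 0, epsilon 1 | 84 |
| Default option, correlation 0, epsilon 0.5 | 142 |
| SPSS-type option, lambda = f²(N − k)(m − 1)·epsilon, epsilon 1 | 128 |
| SPSS-type option, epsilon 0.5 | 212 |
| Between-groups main effect, lambda = f²·N·m/(1 + (m − 1)rho) | 142 |
| One-way ANOVA at one time point, lambda = f²·N | 210 |

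The default and SPSS-type options, each at epsilon 1 and 0.5, thus span 44 to 212. A harsher noncentrality for the interaction, lambda = f²·N·epsilon, gives 250 at epsilon 1 and 418 at epsilon 0.5, still short of 584. Reading 292 as the total does not match any of these either.

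**Power at the stated size.** Under the default option with epsilon = 1, N = 584 gives lambda = 0.0625 × 584 × 6 = 219 and N = 672 gives 252. Power exceeds 0.9999 at both. It also exceeds 0.999 at both totals under the SPSS-type option with epsilon 1 or 0.5.

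**Interaction effect detectable with 95% power at N = 672.**

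- Default, epsilon 1: f = 0.062 (lambda = 0.062² × 672 × 6 = 15.5).
- Default, epsilon 0.5: f = 0.080.
- SPSS-type, epsilon 1: f = 0.107.
- SPSS-type, epsilon 0.5: f = 0.139 (lambda = 0.139² × 670 = 12.9).

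At N = 584 with epsilon 1 the figures are 0.066 (default) and 0.115 (SPSS-type).

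**Simple two-group figure, for orientation only.** d = (1.960 + 1.645) × √(2/n). With n = 336 per arm, d = 0.28. With 336 × 0.85 = 285.6, about 286 per arm, d = 0.30.

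**Benchmarks.** f = √(η²/(1 − η²)) turns the SAP's cut-offs of 0.01, 0.06 and 0.14 into f = 0.10, 0.25 and 0.40. This agrees with section 3.3, which calls 0.25 medium, and conflicts with the d / f line in section 4, which puts medium at 0.50.

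**The case against.** The error runs in the safe direction: more students were planned than the stated inputs require. No estimate, error rate or eligibility rule depends on 292. Section 3.1 describes the trial as already conducted and section 4.3 reports losses already seen, so recruitment cannot change. All of this stands, and it limits the point to a reporting defect.

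The figure of 44, and with it the 13-fold gap, rests on two settings the plan does not state. That also stands, which is why the range is given. Section 4.1 itself allows for a sphericity violation, so epsilon below 1 is a fair alternative. No setting tried closes the gap.

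A plain two-group comparison at d = 0.30 (f = 0.15) needs 289 per group by the normal approximation, or 290 by one-way ANOVA. That is close to 292, but neither input appears in the documents, so it is only a possible origin.

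A reader might go further and infer any of three things, none of which the documents support:

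- **That the trial is underpowered.** The reverse is true for f = 0.25.
- **That it was really sized for an effect about a quarter of the stated one.** The f of 0.066 at 584 is back-solved, no section says it was the planning value, and it becomes 0.115 under the SPSS-type option.
- **That trivially small differences will be significant.** At 336 per arm the smallest significant observed two-group difference is about d = 1.96 × √(2/336) = 0.15, and 95% power needs 0.28, above the SAP's own small benchmark of 0.20. Section 4.1 also requires effect sizes alongside p-values.

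**Conclusion.** Wrong as written. The inputs in section 3.3 require 44 participants in total under the default option with epsilon = 1, and at most about 212 when those two unstated settings are varied, against a stated 584. The 0.95 is not the trial's power for f = 0.25, which exceeds 0.999 at the planned size under those settings, and the basis for 292 per group is undocumented. Confidence in the mismatch is high, because it survives every convention tried. The exact ratio depends on the assumed settings. The d / f benchmark line is a minor inconsistency: sections 4.1 and 4.2 report partial eta squared and d, never f, so no planned result is read against it.

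**What to change.** 1. In section 3.3, state the inputs that actually produced 292 per group, including epsilon and the effect-size option.
2. If they cannot be recovered, remove the claim that f = 0.25 requires 292 per group. Report instead the sensitivity of the planned time-by-group interaction test at the number actually randomized, with assumptions. If that number is 672, 95% power corresponds to f of about 0.062 (default, epsilon 1), 0.080 (default, epsilon 0.5) or 0.107 (SPSS-type, epsilon 1). Do not supply a planning rationale after the fact.
3. A Week 13 two-group figure (d of about 0.28 at 336 per arm, 0.30 at 286) may be added as an aid to readers, labelled as not the planned primary test.
4. In section 4, delete the reference to f from the Cohen's d line, or give f its own benchmarks of 0.10, 0.25 and 0.40.

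The cost is a text correction, with no added participants, data or analyses of outcomes.

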3.5 Randomization and Blinding

Randomization: Following completion of baseline assessments, participants were randomly allocated in a 1:1 ratio using a **computer-generated random sequence**, stratified by academic program to ensure balanced group representation.

Allocation Concealment: Maintained through **sequentially numbered, opaque, sealed envelopes** prepared by an independent researcher not involved in recruitment or assessment.

Blinding: Outcome assessors and data analysts were blinded to group allocation throughout the study. Blinding was maintained during the scoring and data analysis processes.

Contamination Control: Participants were instructed not to share intervention materials, simulation access, or case content with peers assigned to the alternate study condition during the study period.

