4.3 Missing Data

Six participants (three per group) were lost prior to the Time 3 follow-up assessment. Missing follow-up values for participants lost prior to the Time 3 assessment were handled using the **Last Observation Carried Forward (LOCF)** method in accordance with the intention-to-treat principle. Specifically, the most recent available participant outcome values were carried forward for follow-up analyses to preserve randomized group allocation and maintain complete repeated-measures datasets for statistical analysis.

Participants who withdrew from intervention participation permitted retention and analysis of previously collected de-identified study data in accordance with the approved consent process and institutional ethics approval.

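### Section 3.3: a target of 336 per group does not keep the stated minimum of 292 at 15% attrition; it leaves about 285–286 (minor, wrong as written)

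*Combined protocol and SAP*

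**What the plan says.** Section 3.3 (Sample Size Determination) gives the result of the power calculation as "Calculated minimum sample: 292 participants per group". It then gives "Final target enrollment: 336 participants per group (accounting for an anticipated 15% attrition rate", and from this a "total sample size of 672 participants". It prints no formula for the step from 292 to 336.

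Section 3.5 says that "participants were randomly allocated in a 1:1 ratio", so the two groups share one target. On what happened, section 4.3 reports: "Six participants (three per group) were lost prior to the Time 3 follow-up assessment". No section gives the number actually randomised in each group; 336 appears only as a target.

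**The concern.** An attrition rate is the share of those enrolled who are later lost. An enrolment target that accounts for a 15% rate should therefore still leave the calculated minimum once 15% of the target has gone. Here it does not. The three figures in section 3.3 (292, 15% and 336) cannot all stand together on that reading.

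The pattern is a familiar one: 15% of the minimum appears to have been added, where the minimum should have been divided by the retained fraction. What is at stake is whether the sample-size paragraph is correct, since readers will check it and it is likely to be carried into the trial report. The same step, if reused, would also under-inflate any revised minimum.

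**Working it through.** **Inputs, all from section 3.3:** minimum 292 per group; anticipated attrition 15%; target 336 per group, 672 in total. From section 4.3: three lost per group before Time 3.

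**1. Reproduce the printed target.** Minimum × (1 + rate) = 292 × 1.15 = 335.8, which rounds to 336. This matches. Minimum ÷ (1 − rate) = 292/0.85 = 343.5, which does not. The multiplication is thus the likely route, but it is an inference.

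**2. Apply the stated attrition to the printed target.** 336 × 0.85 = 285.6 per group, so 285–286 remain. The shortfall against 292 is 6–7 per group. In total, 672 × 0.85 = 571.2 against 2 × 292 = 584. This step does not depend on how 336 was obtained.

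**3. Find the target that would keep 292.**
- 343 × 0.85 = 291.55, just short.
- 344 × 0.85 = 292.4, enough.

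So 344 per group, or 688 in total. That is 8 more per group and 16 more in total than planned (8/336 = 2.4%).

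**4. Find the loss that 336 can absorb.** 1 − 292/336 = 0.131, or about 13.1%.

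**5. Compare with the reported loss.** If exactly 336 were randomised per group, three losses are 3/336 = 0.9% and leave 333. The condition matters, because the documents do not confirm it.

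**6. Ask whether stated power is lost.** Section 3.3 lists a within-between interaction, f = 0.25, α = 0.05, power 0.95, 2 groups, 3 occasions and correlation 0.5. With N the total sample and m = 3 occasions:
- noncentrality λ = f² × N × m/(1 − ρ) = 0.0625 × N × 3/0.5 = 0.375N
- degrees of freedom: (2 − 1)(3 − 1) = 2 and 2(N − 2)

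| N in total | λ | df | Power |
|---|---|---|---|
| 42 | 15.75 | 2, 80 | 0.946 |
| 44 | 16.5 | 2, 84 | 0.956 |
| 570–572 | about 214 | 2, 1136–1140 | above 0.999 |

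The listed inputs therefore need 44 in total (22 per group). Other effect-size conventions or tests applied to the same inputs need 126 to 210 in total; none gives 292, per group or in total. At 570–572 completers, power is above 0.999 under every one of them.

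**The case against.** **The allowance was never tested.** The trial has been conducted, and six losses are reported in total. No analysis, estimate or conclusion depends on what 15% attrition would have done. This stands, and it is why the point is minor. It does not make the sentence in section 3.3 true.

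**The analysed number does not fall with attrition.** The opening of section 4 includes everyone randomised, and section 4.3 carries the last value forward for those missing at Time 3. It is right that 285–286 describes participants observed at Time 3 and not the planned analysis set. But carrying values forward keeps rows in the dataset; it does not replace lost observations, so it does not rescue the allowance.

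**The gap is only rounding.** It is not. The inputs are one integer and one percentage, with no iterative software step between 292 and 336.

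**The authors may have meant a 15% uplift.** Section 3.3 does not say in so many words that 292 are to remain after loss; that is the natural reading of a minimum followed by an attrition allowance. If an uplift was meant, calling it an attrition rate still needs correcting.

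**Stronger readings that the documents do not support.**
- A reader might infer that the slip lowers power, for example to 94.6% at 286 per group. That figure holds only if 292 per group gives exactly 95% power, and the inputs in section 3.3 contradict this.
- A reader might take 333 per group as the number retained at Time 3. That requires exactly 336 randomised per group, which no section states.

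**Conclusion.** Minor, and wrong as written. The target of 336 per group does not account for 15% attrition on a minimum of 292. It falls short by 6–7 per group after loss, or by 8 per group (16 in total) at enrolment. The loss that it can absorb is about 13.1%.

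This rests on two things: that attrition means a share of those enrolled, and that 292 is the number to be kept. It does not rest on the inferred multiplication by 1.15.

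The slip costs no stated power. The more serious problem in section 3.3 is that 292 cannot be reproduced from the listed inputs. That is a separate matter, and resolving it would not by itself correct the inflation step.

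**What to change.** In section 3.3, restate that the target of 336 per group would leave about 285–286 per group at the anticipated 15% attrition, and that 292 is kept only up to about 13% loss. Leave the 15% in place as the planning assumption; it should not be replaced by 13% now that the actual loss is known. No enrolment needs to be added.

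Alongside section 4.3, report the numbers actually randomised and actually observed at Time 3 in each group. Give 333 per group only if the records show that 336 per group were randomised.

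Correct or explain the origin of 292 separately, and inflate any new minimum by dividing by (1 − 0.15).

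The cost is one sentence in section 3.3 and a line of counts. No data or analysis changes; the stated allowance becomes slightly less favourable.

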3.4 Eligibility Criteria

Inclusion Criteria:

- Undergraduate students enrolled in health science programs (Physiotherapy, Occupational Therapy, Nursing, Allied Health Sciences)
- Registered for a Human Physiology course during the study period
- Age between 18 and 25 years
- Proficient in English
- Access to an internet-enabled personal device capable of supporting web-based educational applications

Exclusion Criteria:

- Students with prior formal exposure to structured simulation-based physiology instruction or adaptive digital learning platforms (to minimize potential contamination effects)

3.5 Randomization and Blinding

Randomization: Following completion of baseline assessments, participants were randomly allocated in a 1:1 ratio using a **computer-generated random sequence**, stratified by academic program to ensure balanced group representation.

Allocation Concealment: Maintained through **sequentially numbered, opaque, sealed envelopes** prepared by an independent researcher not involved in recruitment or assessment.

Blinding: Outcome assessors and data analysts were blinded to group allocation throughout the study. Blinding was maintained during the scoring and data analysis processes.

Contamination Control: Participants were instructed not to share intervention materials, simulation access, or case content with peers assigned to the alternate study condition during the study period.

